## 7.1 Patient Randomization

### Part 1

It was planned that approximately 320 eligible patients would be randomized, in order to obtain 306 evaluable patients (i.e., patients who received any test drug and have at least one post-surgical pain intensity score). It had been estimated that 4% of randomized patients may not receive any test drug due to unforeseeable intra-operative exclusion. Patients would be randomized in a 1:1 ratio to receive one of two treatments based on a computer-generated randomization schedule prepared before the study:

- Treatment Group 1: SABER®-Bupivacaine 5 mL (POSIMIR®)(132 mg/mL, 660 mg bupivacaine base)
- Treatment Group 2: Sterile normal saline 5 mL (0.9% sodium chloride injection, USP) (placebo)

Due to the early administrative stopping, only approximately 90 subjects will be enrolled and randomized in Part 1.

Part 2

Approximately 274 eligible patients will be randomized, in order to obtain 264 evaluable patients (i.e., patients who received any test drug). It has been estimated that 4% of randomized patients may not receive any test drug due to unforeseeable intra-operative exclusion such as conversion to open cholecystectomy or need for a fifth port. Patients will be randomized in a 1:1 ratio to receive one of two treatments based on a computer-generated randomization schedule prepared before the study:

- Treatment Group 3: SABER®-Bupivacaine 5 mL (POSIMIR®)(132 mg/mL, 660 mg bupivacaine base)
- Treatment Group 4: Bupivacaine HCl without epinephrine, 15 mL of 0.5% solution (75 mg)

CCI

Following screening and confirmation of eligibility, an interactive web response system (IWRS) will be used to assign patients to a treatment group. The IWRS will confirm randomization via automatic notification to the investigative site.

If all Screening (i.e. pre-operative) Inclusion/Exclusion criteria have been met, randomization can be done up to 1 business day prior to surgery. In the event that a randomized patient does not have the surgical procedure for unforeseen circumstances (see [Section 5.3.3](#)) or does not receive any test drug, replacement of the patient has been planned. The IWRS system will be algorithmically instructed to issue the appropriate randomization replacement and to ensure the balance of treatment as planned. Precise details on the IWRS algorithm have been described in the IWRS specifications.

CCI

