##### 9.2.1.2 Solicited Patient-Reported Adverse Events

The solicited patient-reported AEs that must be recorded at specified times on the LogPad (see [Table 2](#)) are: dizziness, somnolence (drowsiness), constipation, nausea, vomiting, pruritus

(itching), headache, Dysgeusia (metallic taste in mouth), paresthesia (tingling or pins and needles), and hypoesthesia (numbness) (see [Section 7.5](#)).

These ten adverse events were chosen for detailed study by solicitation on the LogPad for two reasons. First, many of these AEs are common symptoms associated with opioid administration ([Zhao et al, 2004](#); [Daniels et al, 2009](#); [YaDeau et al, 2011](#)). If treatment with SABER®-Bupivacaine results in a reduced consumption of rescue opioids compared to placebo or bupivacaine HCl, there may also be a concomitant reduction in the incidence of these adverse events. This reduction in opioid-related adverse events could then be regarded as an additional benefit of SABER®-Bupivacaine treatment.

CCI

If the patient reports an AE on the LogPad investigative site personnel will receive an alert. At each point of contact, investigative site personnel will follow-up with the patient regarding severity, frequency, duration and action taken of any AEs reported on the LogPad and appropriately document this data and causality in the source and AE eCRF.

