### **11.10 Statistical Analysis of Safety Endpoints**

#### **11.10.1 Safety Variables and Summaries**

Safety summaries will be based on the safety population. The safety population will include all subjects treated with SABER®-Bupivacaine 5 mL (660 mg bupivacaine base) or 0.9% sterile normal saline 5 mL (placebo) in Part 1; and all subjects treated with SABER®-Bupivacaine 5 mL or 15 mL of 0.5% bupivacaine HCl in Part 2. It will include summaries in the form of tables and patient listings by three treatment arms; SABER®-Bupivacaine 5 mL (660 mg bupivacaine base), 15 mL of 0.5% solution bupivacaine HCl (75 mg) or 0.9% sterile, normal saline 5 mL (placebo).

Safety variables include:

- Subject incidence rate of adverse events (both pre-specified patient-reported AEs solicited on LogPad through Study Day 4 [POD 3], as well as spontaneous AEs reported either by patient or investigator)

- Subject incidence rate of solicited AEs occurring in the first 6 hours after dosing of test drug.
- Time to the first occurrence of the solicited AEs
- Time to PACU discharge
- Change in standard 12-lead ECG at Screening, Visit 6 (Study Day 29), and Visit 7 (Study Day 60)
- Change in safety Laboratory Tests (serum chemistry, hematology, urinalysis) (Screening, Study Day 4, Study Day 29, Study Day 60)
- Change in vital Signs (heart rate, blood pressure, temperature, respiratory rate) (at each scheduled visit) and height, weight, BMI (Screening, Study Day 29, Study Day 60)
- CCI 

The subject incidence rate (number and percentage) of treatment emergent adverse events will be tabulated in each treatment group by MedDRA System Organ Class and Preferred Term. Summaries will also be presented by the severity of the adverse event and by relationship to test drug.

The individual rate of solicited patient-reported AEs (dizziness, somnolence, constipation, nausea, vomiting, pruritus, headache, dysgeusia, hypoesthesia, and paresthesia) will be derived. The risk ratio and 95% confidence interval (CI) for the individual AE rate will be presented with saline placebo and bupivacaine HCl as the control groups. For example, if the 95% CI for the risk ratio contains 1, the AE risk is considered comparable between the active and control groups.

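### For solicited AEs, a risk-ratio CI that contains 1 is read as showing comparable risk, with no margin

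*Combined protocol and SAP*

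**What the plan says.** Section 11.10.1 (Safety Variables and Summaries) covers ten solicited events: "The individual rate of solicited patient-reported AEs (dizziness, somnolence, constipation, nausea, vomiting, pruritus, headache, dysgeusia, hypoesthesia, and paresthesia) will be derived". For each one, the risk ratio and its 95% CI "will be presented with saline placebo and bupivacaine HCl as the control groups". The next sentence, which opens as an example, gives the reading rule: "if the 95% CI for the risk ratio contains 1, the AE risk is considered comparable between the active and control groups". The visible text has no margin, no limit on CI width and no power statement for these comparisons.

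Safety results are shown "summaries in the form of tables and patient listings by three treatment arms", so SABER-Bupivacaine patients from Parts 1 and 2 form one arm. Section 7.1 says that "only approximately 90 subjects will be enrolled and randomized in Part 1", which leaves the saline group small.

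Section 9.2.1.2 explains why these events are solicited: "many of these AEs are common symptoms associated with opioid administration". If rescue opioid use falls, these events may fall too, and "This reduction in opioid-related adverse events could then be regarded as an additional benefit of" the test drug.

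For surgical-site AEs, section 11.10.1 also plans risk ratios with 95% CIs but attaches no comparability label. The rule is not stated for SAEs either. Both are outside this point.

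**The concern.** A 95% CI that contains 1 means only that the data do not exclude equal risk at the two-sided 5% level. It does not mean that they exclude a material increase. Under the rule, when the true risks differ, a smaller sample or a rarer event makes the comparable label more likely.

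What is at stake is how the safety results are read. Section 9.2.1.2 is ready to count a reduction in these events as a benefit, while section 11.10.1 would report an imprecisely estimated increase as comparable risk. The exposure is greatest for the less common solicited events and for the saline comparison.

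**Working it through.** **The plan's own figure.** None exists for this comparison. The 132 per arm in section 11.2 comes with 90% power, which the synopsis ties to pain on movement. The effect size is redacted, so 132 cannot be reproduced from stated inputs. A standardised effect of 0.40 would give it, but that says nothing about AE risk.

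**Inputs**
- Bupivacaine HCl: 132 (section 11.2).
- Saline: about 90/2 = 45 (section 7.1, 1:1 allocation, all assumed dosed).
- SABER-Bupivacaine: 132 + 45 = 177 (both Parts in one safety arm).
- Control AE rates: not given, so 5% to 30% is assumed.
- CI method: not named, so log-Wald is assumed, with 0.5 added to each cell if either event count is zero.

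**Step 1: the effect of sample size alone.** The log-Wald interval is exp(ln RR ± 1.96 × SE), with SE² = (1−p₁)/(n₁p₁) + (1−p₀)/(n₀p₀). For rates of 20% v 10% and n per arm, SE² = (4 + 9)/n = 13/n and ln 2 = 0.693.

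| n per arm | SE | 95% CI for RR 2.0 | Label |
|---|---|---|---|
| 132 | 0.314 | 1.08 to 3.70 | not comparable |
| 80 | 0.403 | 0.91 to 4.41 | comparable |
| 40 | 0.570 | 0.65 to 6.11 | comparable |

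The rates are identical, yet the label changes as data are removed. (At 132 the rates do not give whole counts; that row is the formula evaluated at those rates.)

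**Step 2: how often a real increase is labelled comparable.** Every pair of event counts was enumerated, weighted by independent binomial probabilities, and summed where the CI contained 1.

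| True RR, control | 5% | 10% | 15% | 20% | 30% |
|---|---|---|---|---|---|
| 1.5, bupivacaine HCl | 89% | 77% | 64% | 51% | 24% |
| 2.0, bupivacaine HCl | 67% | 34% | 13% | 3% | <0.1% |
| 1.5, saline | 99.5% | 96% | 88% | 81% | 64% |
| 2.0, saline | 99.7% | 77% | 55% | 34% | 7% |

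For a doubling, the chance passes 50% below a control rate of about 7% (bupivacaine HCl) or 16% (saline). For a 1.5-fold increase, the crossovers are about 20% and 37%. A tripling against bupivacaine HCl is labelled comparable 18% of the time at a 5% control rate and under 1% at 10%.

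**Step 3: dependence on the CI method.** A score interval contains 1 when the pooled two-proportion |z| is at most 1.96. With that rule, the saline figures at the same five rates become 88/67/45/26/4% for a doubling and 96/89/82/74/55% for a 1.5-fold increase. For a doubling against bupivacaine HCl they become 62/32/12/3/<0.1%.

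**Step 4: observed results.** 16/132 v 8/132 has SE = √(1/16 − 1/132 + 1/8 − 1/132) = 0.415, so RR 2.00 (0.89 to 4.51). Its pooled z is 1.71, so either method labels it comparable. Other cases sit on the edge under log-Wald: 21/177 v 7/132, RR 2.24 (0.98 to 5.11); 46/177 v 5/45, RR 2.34 (0.99 to 5.54); 65/177 v 9/45, RR 1.84 (0.99 to 3.40). Their pooled z values are 1.99, 2.12 and 2.13, so a score interval would not label them comparable. With the method unnamed, the label itself is undetermined for such results.

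**Step 5: what equal observed rates would exclude.** With p₁ = p₀ = p, the upper limit is exp(1.96 × √[((1−p)/p)(1/n₁ + 1/n₀)]).

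| Observed rate in both arms | 5% | 10% | 20% | 30% |
|---|---|---|---|---|
| Upper limit, bupivacaine HCl | 2.67 | 1.97 | 1.57 | 1.41 |
| Upper limit, saline | 4.16 | 2.67 | 1.92 | 1.65 |

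Even a perfectly null result at a 10% rate leaves a near doubling (bupivacaine HCl) or more (saline) inside the interval.

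**The case against.** The strongest reply is that little depends on the sentence. It is offered as an example, and the risk ratio, CI and event percentages will be reported anyway, so a reader would see an RR of 2.34 with its interval beside any label. The gate-keeping sequence in section 11.8.4 covers efficacy endpoints only, and stopping under section 11.9.1 rests on committee review of SAEs. The rule is also symmetric: an imprecise reduction would be called comparable as well. All of this stands and limits the weight of the point. It does not make the inference valid, and an example of a wrong inference still tells the report's authors how to write the conclusion.

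Parts of sections 9.2.1.2 and 11.10.1 are redacted, and section 11.6 refers to a separate detailed SAP, so this is the only *visible* rule and a margin elsewhere cannot be excluded. But the visible criterion is complete as written, and a margin elsewhere would conflict with it.

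The saline probabilities depend on the CI method, as step 3 shows. The 99.7% at a 5% control rate is partly a small-count artefact of log-Wald: it exceeds the 99.5% for the smaller 1.5-fold increase. Section 7.1 allows 4% not dosed, so 45 × 0.96 ≈ 43 saline patients is more consistent than 45; the effect is small.

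**Conclusion.** The concern holds. The stated rule treats a non-significant difference as comparable risk for ten AEs and two comparators. Its effect is negligible for a doubling of a common AE against bupivacaine HCl (3% at a 20% control rate). It is substantial for a 1.5-fold increase there (about half at 20%), for uncommon events, and for the saline comparison: at a 10% control rate a true doubling is labelled comparable 77% of the time with log-Wald and 67% with a score interval.

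These sizes rest on assumed control rates, about 45 Part 1 patients per arm, pooling of SABER-Bupivacaine across Parts, and independent binomials. Using Part 2 alone (132 v 132) changes little: at a 10% control rate, 79% for a 1.5-fold increase and 39% for a doubling. The logical error depends on none of these assumptions. It affects safety interpretation, not the primary test, and should be corrected before unblinding.

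**What to change.** Delete the comparability sentence from section 11.10.1. Report the risk ratio with its 95% CI as an estimate, name the CI method, and state that an interval containing 1 does not show comparable risk. This matches what the section already does for surgical-site AEs. A risk difference with its CI is a useful addition but not essential.

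If a comparability statement is wanted, require the upper 95% limit to lie below a margin justified and fixed before unblinding. That would often fail even with equal true risks. By normal approximation on the log risk ratio, at AE rates of 10/20/30%, the chance that the upper limit falls below an illustrative margin of 2.0 is 52/85/98% against bupivacaine HCl and 28/55/78% against saline. For a margin of 1.5 against bupivacaine HCl it is 22/42/64%.

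The cost is one sentence of wording and, if adopted, one table column. Section 11.11 already provides for documenting such changes before unblinding. Sample size and data collection are unchanged. The sponsor gives up an automatic comparable label.

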### 9.3.4 Serious Adverse Events of Special Interest

Based on previous clinical experience, three serious adverse events are being pre-specified for close monitoring. The following pre-specified surgical wound complications, when reported as SAEs, are of special interest to DURECT CCI [REDACTED] (see [Section 9.2.6](#) for detailed definitions):

- 1) Wound dehiscence reported as an SAE
- 2) Wound hematoma reported as an SAE
- 3) Surgical site infection reported as an SAE

The sponsor medical monitor will carefully monitor the blinded safety data for any occurrence of these pre-specified SAEs. SAEs of special interest will be reported both to the Safety Assessment Committee (SAC), CCI [REDACTED] and to the FDA in accordance with safety reporting regulations. The expected incidence rate of the individual SAEs of special interest will be less than 1% based on the previous clinical experience with SABER-Bupivacaine and the published literature ([Richards et al, 2003](#); [Fahrner et al, 2014](#); [Keus et al, 2009](#); [Shea et al, 1996](#)). Non-serious instances of these surgical wound complications will be analyzed as AEs (as described in [Section 9.2.6](#) and [9.3.2](#))

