Time to the first occurrence of the solicited AEs will be analyzed by the Kaplan Meier method. For subjects who do not have the AE, the observation will be censored in the analyses. Median time and 95% confidence interval (CI) will be determined.

The change in safety laboratory, ECG and vital signs parameters from baseline will be analyzed by shift tables. Descriptive statistics (means, medians, SD, minimum/maximum) for the safety variables and change from baseline will be summarized. Subjects found to have abnormal safety values considered clinically significant will be summarized.

The presence/absence of surgical site AEs (see definitions in [Section 9.2.6](#)) will be tabulated by treatment and study visit. The overall rate of each AE across study visits will be tabulated by treatment. The risk ratio and 95% CI will be derived for each AE. Known risk factors related to wound healing, such as being diabetic or having higher BMI, may be used for adjusted relative risk if they are not balanced by randomization alone. Time to the first occurrence of each AE

will be derived from the end of surgery. The data will be censored for subjects who do not have the AE. The median, 95% CI, 25th and 75th percentile for the time to each AE will be summarized by treatment. The time to resolution of each AE will also be derived and summarized.

CCI

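### For rare surgical-site adverse events, the risk ratio in Section 11.10.1 will often be undefined or zero and the time-to-event quantiles will almost never be reached, so a between-arm effect size with an interval may be lost.

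*Combined protocol and SAP*

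**What the plan says.** Section 11.10.1 sets out four summaries for surgical-site adverse events:

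- presence or absence, which "will be tabulated by treatment and study visit";
- a crude rate: "The overall rate of each AE across study visits will be tabulated by treatment";
- a between-arm comparison: "The risk ratio and 95% CI will be derived for each AE";
- time to first event, where the median with its 95% CI and the 25th and 75th "percentile for the time to each AE will be summarized by treatment". On event-free patients: "The data will be censored for subjects who do not have the AE".

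The risk ratio may be adjusted for wound-healing risk factors. For the solicited events, the same section says that risk ratios "will be presented with saline placebo and bupivacaine HCl as the control groups". Safety tables use three treatment arms, so SABER-Bupivacaine patients from Parts 1 and 2 form one arm.

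On frequency, Section 9.3.4 says of serious wound dehiscence, hematoma and surgical-site infection: "The expected incidence rate of the individual SAEs of special interest will be less than 1" percent. It adds: "Non-serious instances of these surgical wound complications will be analyzed as AEs". No rate is given for those.

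Section 11.5 allows 95% intervals where appropriate, and exact tests such as Fisher's when cell counts are small. Section 11.6 applies Kaplan-Meier to any time-to-event variable. The readable text has no zero-cell rule for the ratio, no risk difference, and no rule for a quantile that is not reached.

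**The concern.** A risk ratio divides by the control rate. With no control event it has no finite value; with no event in the SABER-Bupivacaine arm it is zero, and the usual log-scale interval does not exist. The small-cell provision in Section 11.5 changes the test, not the estimate. The time quantiles have a similar limit: with event-free patients censored, the Kaplan-Meier curve must reach 25% cumulative incidence before the first quartile exists.

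The awkward case is also the one of most interest, with events on SABER-Bupivacaine and none on control. The report would then show counts and rates, but the planned ratio could not say how large the excess might be. A repair chosen after unblinding (a continuity correction, dropping the row, switching measure) would be post hoc.

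**Working it through.** **Arm sizes.** Section 11.3 plans 264 evaluable patients in Part 2, randomized 1:1, hence 132 per arm. The inflation for 4% not dosed gives 264 / 0.96 = 275, against 274 stated, so the plan's figure reproduces to rounding. Part 1 has about 90 patients, 1:1, hence about 45 per arm. The pooled SABER-Bupivacaine arm is about 132 + 45 = 177, with HCl 132 and saline 45.

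**Risk ratio.** For a true rate p, P(no event in an arm of n) = (1 − p)^n. The ratio is undefined or zero when either arm has no event, with probability 1 − (1 − P0 SABER)(1 − P0 control). At p = 1%:

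- 0.99^177 = 0.169, 0.99^132 = 0.265, 0.99^45 = 0.636
- against HCl: 1 − 0.831 × 0.735 = 0.39
- against saline: 1 − 0.831 × 0.364 = 0.70

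| True rate, all arms | No event: SABER / HCl / saline | Undefined or 0 v HCl | Undefined or 0 v saline |
|---|---|---|---|
| 0.5% | 41% / 52% / 80% | 72% | 88% |
| 1% | 17% / 27% / 64% | 39% | 70% |
| 2% | 3% / 7% / 40% | 10% | 42% |
| 5% | 0.01% / 0.1% / 10% | 0.1% | 10% |

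Only the bound of 1%, for the serious forms, comes from the plan. The other rows are assumed values that show the range.

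**Events on SABER-Bupivacaine, none on HCl.** At 1% in both arms the probability is 0.265 × (1 − 0.169) = 0.22. With a true excess of 3% v 1%, P(at least 2 of 177 at 3%) = 1 − 0.97^177 − 177 × 0.03 × 0.97^176 = 0.97. The chance of at least 2 SABER-Bupivacaine events with none on HCl is then 0.97 × 0.265 = 0.26.

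**Time quantiles.** With little censoring before Day 60 (an assumption), the q-quantile needs about q × n patients with the event. For the 25th percentile that is 45 of 177, 33 of 132 or 12 of 45; for the median it is 89, 66 or 23. At a true rate of 10%, the binomial chance of 12 or more events in 45 is 0.12%, and it is far smaller in the larger arms. At 1% it is effectively zero.

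**What a risk difference would give.** The Newcombe interval has lower limit d − √[(p1 − l1)² + (u2 − p2)²] and upper limit d + √[(u1 − p1)² + (p2 − l2)²], where l and u are the Wilson limits of each arm.

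- 5/177 v 0/132: d = 2.8 points; Wilson limits 1.2% to 6.4% and 0% to 2.8%; interval −0.4 to 6.4 points.
- 5/132 v 0/132: d = 3.8 points; Wilson limits 1.6% to 8.6% and 0% to 2.8%; interval 0.2 to 8.6 points. Fisher's exact p = 0.06.

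The ratio has no finite value in either example, and the difference has an interval in both. The first example uses the planned pooled arm; the second uses 132 v 132.

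**The case against.** A reader might infer that these events would receive no estimate, or that the ratio cannot be computed for rare events. The documents do not support either reading. Counts by visit and rates by arm are planned in the same section, and Section 11.5 supplies intervals where appropriate and exact tests for sparse cells. At a 1% rate the ratio against HCl is finite and non-zero in about 61% of trials, and at 2% in about 90%. Section 11.10.1 names no interval method for the ratio: a score interval for 5/132 v 0/132 would still have a lower limit of about 1.3, with no upper limit. The 39% figure also includes trials with no SABER-Bupivacaine event, so it is not the probability of a hidden harm signal; that component is about 22%.

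Three further points stand. The bound of 1% covers only the serious forms, while the section covers all surgical-site events, including bruising and drainage, which may be common enough for the ratio to work. Surveillance of serious events does not depend on these tables: Sections 9.3.4 and 11.9.1 provide for medical-monitor review, review by the Safety Assessment Committee, and stopping criteria. Kaplan-Meier is already the planned method for time-to-event variables, so an unreached quantile would normally be shown as not estimable, which loses information but is not an error.

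These points limit the scope but leave the gap. Exact tests and per-arm intervals do not give an effect size between arms, and no readable rule says what replaces the ratio or the quantiles. Text redacted around this section, or the separate SAP named in Section 11.6, may hold such a rule; this cannot be checked.

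**Conclusion.** The concern holds for rare surgical-site events. If the true rate is 1% in each arm, the planned ratio fails in 39% of trials against HCl and 70% against saline. It fails more often below 1%, and rarely against HCl at 5%. The failure of the time quantiles is close to certain for any event at or below 10%. The possible loss is confined to the between-arm effect size with its interval and to an informative time summary.

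The conclusion rests on arms of about 177, 132 and 45, on equal true rates except in the 3% v 1% example, on independent patients, and on near-complete follow-up. It does not extend to commoner surgical-site events, or to the solicited events, for which no sparsity is shown.

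**What to change.** In Section 11.10.1, before unblinding:

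- Keep the counts, rates and risk ratio. For each surgical-site event add the risk difference with a Newcombe or Miettinen-Nurminen 95% CI, and name it as the reported comparison when either arm has no events or very few. State the threshold for very few in advance.
- Report Kaplan-Meier cumulative incidence by arm with 95% CI at Study Days 4, 8, 15, 29 and 60, and give the median and quartiles only when they are reached. Print the number at risk, because Section 7.4.10 exempts patients enrolled before approval of Amendment 5 from the Day 60 visit.
- The same addition for solicited events is optional.

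The cost is wording and a few table columns, with no new data. The downside is one more effect measure per event, whose interval may occasionally disagree with Fisher's exact test, as in the 132 v 132 example. The text should say that the interval describes the size of the difference and is not a second test.
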